### **7.1.2 Serious Adverse Events (SAEs)**

A serious adverse event (SAE) is any AE that meets one of the following conditions:

- Death during the period of surveillance defined by the protocol;
- Is immediately life-threatening (e.g., participant was, in the view of the Investigator, at immediate risk of death from the event as it occurred). This does not include an AE that, had it occurred in a more serious form, might have caused death;
- An event requiring inpatient hospitalization or prolongation of existing hospitalization during the period of protocol defined surveillance (including any overnight stay in the hospital, regardless of the length of stay, even if the hospitalization is only a precautionary measure to allow continued observation. However, hospitalization (including hospitalization for an elective procedure) for continued treatment or assessment of a pre-existing condition that has not worsened, does not constitute an SAE. NOTE: Evaluation in a physician's office, or at a hospital or other urgent care setting in an observational, non-admitted status regardless of the time period of observation, does not constitute an SAE;
- Results in congenital anomaly or birth defect;
- Results in persistent or significant disability/incapacity or substantial disruption of the ability to conduct normal life functions;
- Is an important medical event that may not result in death, be life threatening, or require hospitalization, but based upon appropriate medical judgment, may jeopardize the participant and may require medical or surgical intervention to prevent one of the outcomes listed above. Examples of such medical events include allergic bronchospasm requiring intensive treatment in an emergency room or at home, blood dyscrasias or convulsions that do not result in inpatient hospitalization;
- Is medically significant or requires intervention to prevent one or other of the outcomes listed above.

### Clarification of Serious Adverse Events

- Death is an outcome of an AE, and not an adverse event in itself
- The participant may not have been on investigational medicinal product at the occurrence of the event.
- “Life-threatening” means that the participant was at immediate risk of death from the event as it occurred. This does not include an event that might have led to death if it had occurred with greater severity
- Complications that occur during hospitalizations are AEs. If a complication prolongs the hospitalization, it is an SAE
- Inpatient hospitalization means that the participant has been formally admitted to a hospital for medical reasons, for any length of time. This may or may not be overnight. Observation status or evaluation in an emergency department, urgent care setting, or outpatient office does not constitute an SAE.
- The investigator will attempt to establish a diagnosis of the event on the basis of signs, symptoms, and/or other clinical information. In such cases, the diagnosis will be documented as the AE and/or SAE and not the individual signs/symptoms.

Serious adverse events that are ongoing should be followed until resolution. The reporting period for SAEs is described in Section 9.6.2.

#### **7.1.3 Unexpected Adverse Drug Reactions**

An unexpected adverse drug reaction is a reaction for which the nature or severity is not consistent with the applicable product information (see Investigator’s Brochure). Until product information is amended, expedited reporting is required for additional occurrences of the reaction. Reports that add significant information on specificity or severity of a known, already documented SAE constitute unexpected events.

#### **7.1.4 Assessing Severity (Intensity)**

The Investigator will grade laboratory AEs and clinical AEs (based on discussions with study participants) using the NCI Common Terminology Criteria for Adverse Events v5.0:

- Mild (Grade 1)
- Moderate (Grade 2)
- Severe (Grade 3)
- Life-threatening consequences (Grade 4)
- Death related to AE (Grade 5)

Adverse events will be recorded on the eCRF at the severity reported by the investigator.

If an ongoing AE worsens or increases in its severity or its relationship to the study drug changes, a new AE entry for the event should be entered on the eCRF.

The following is a link to the grading scale:

[https://ctep.cancer.gov/protocolDevelopment/electronic\\_applications/docs/CTCAE\\_v5\\_Quick\\_Reference\\_5x7.pdf](https://ctep.cancer.gov/protocolDevelopment/electronic_applications/docs/CTCAE_v5_Quick_Reference_5x7.pdf)

#### **7.1.5 Causal Relationship of Investigational Product to Adverse Events**

A causally related AE is one judged to have a suspected relationship to the administration of the investigational agent. Conversely, an AE may also be assessed as not related to the investigational product. The Investigator is responsible for reporting adverse events and judging

the relationship between the administration of the investigational product and an AE because the investigator is knowledgeable about the participant (e.g., medical history, concomitant medications), administers the investigational product, and monitors the participant's response to the investigational product. The Sponsor will assess the overall safety of the investigational product and determine whether expedited reporting to regulatory agencies is indicated.

Investigators should use their knowledge of the Study Participant, the circumstances surrounding the event, and an evaluation of any potential alternative causes to determine whether or not an adverse event is considered to be related to the study drug by the following criteria:

- Related – the investigator considers that there is a causal relationship between the event and study drug;
- Probably related – the Investigator considers that there is a probability of a causal relationship of the event to the study drug
- Possibly related – the investigator considers that there is a possible causal relationship of the event to the study drug
- Not related – the investigator considers that the event has no relationship to administration of the study drug

The following guidance should also be taken into consideration:

- Temporal relationship of event to initiation of study drug;
- Course of the event, discontinuation of study drug, or reintroduction of study drug (when applicable);
- Known association of the event with the study drug or with similar treatments;
- Known association of the event with the disease under study;
- Presence of risk factors in the Study Participant or use of concomitant medications known to increase the occurrence of the event

#### **7.1.6 Abnormal Laboratory Value**

Grade 2 and higher laboratory abnormalities (e.g., serum chemistry, CBC) are to be recorded.

Any laboratory abnormality that is new in onset or worsened in severity or frequency from the baseline condition and meets one of the following criteria will be recorded as an AE:

- Requires therapeutic intervention or diagnostic tests
- Leads to discontinuation of study treatment
- Has accompanying or inducing symptoms or signs
- Is judged by the investigator as clinically significant

#### **7.1.7 Pregnancy During Study**

Pregnancy is an exclusion criterion for participation in this study. Women of childbearing potential should either be unable to conceive or use a form of birth control such as a diaphragm, birth control pills, IUD, or regular use of male or female condom. If a participant becomes pregnant during the time of the study, they will be asked to contact study staff after the end of the study to report on the outcome of pregnancy.

---

### **7.1.8 Post-study Reporting Requirements**

All AEs and SAEs including deaths, regardless of cause or relationship, must be reported for participants on study (including any protocol-required post-treatment follow-up).

Investigators are not obligated to actively seek AEs or SAEs beyond the follow up period for participants. However, if the Investigator learns of an AE or SAE that occurs after the completion or termination visit and the event is deemed by the Investigator to be probably or possibly related to the study treatment, he/she should promptly document and report the event to the study team and medical monitor.

### **7.2 Methods and Timing for Collection and Recording of Safety Data**

At the time of each study visit, participants will be queried as to adverse events that have occurred in the interim period and the current status of any AE that was reported at a prior visit that has not yet resolved. As delineated above, both solicited and non-solicited events will be sought. Additionally, labs and ECGs will be reviewed for safety.

All AEs, regardless of severity, seriousness, or presumed relationship to study treatment, must be recorded using medical terminology in source documents and on the eCRF. Whenever possible, a diagnosis will be documented, in lieu of symptoms. The source document and the eCRF must contain the Investigator's opinion concerning the relationship of the AE to study treatment.

AEs should be described with the following attributes:

- Duration (start and end dates)
- Seriousness
- Severity
- Causality
- Action(s) taken
- Outcome

### **7.3 Safety and Toxicity Management**

The Medical Monitor will be responsible for the overall safety monitoring of the study. The site Investigator will be responsible locally for safety.

Safety assessments include the following:

- Incidence of all adverse events classified by system organ class, preferred term, severity, and relationship to study treatment
- Changes in safety laboratory parameters

#### **7.3.1 Events Requiring Expedited Reporting**

Events requiring expedited reporting (ERER) are defined as any Adverse Events including:

- Grade 3 or greater fever;
- Grade 3 or greater systemic symptoms;
- Grade 3 or greater laboratory abnormalities

The most severe grade for that particular event is to be documented in the eCRFs.

Sites will inform the Sponsor of any ERER within 24 hours to discuss whether dosing to the participant should continue.

### **7.3.2 Stopping Rules**

If any of the following situations occur, then further enrollment and Study Treatments will be halted immediately until a thorough investigation has been conducted by the Medical Monitor and Principal Investigator and the IRB (if applicable):

- Three (3) or more participants experience an ERER assessed as related to Study Treatment;
- Any participant experiences a potentially life threatening AE, Grade 4 AE or death assessed as related to Study Treatment;
- Five (5) or more participants across both treatment arms experience the same or similar grade 3 or 4 adverse event, assessed as related to Study Treatment;
- Any report of anaphylaxis of Grade 3 or greater assessed as related to Study Treatment.

Upon conclusion, the sponsor or designee will notify all investigators and the IRB/REC (if required) regarding the outcome of any investigation.

Any SAE or death assessed as related to Study Treatment will lead to an immediate halt of study enrollment and Study Treatments, until the event has been investigated and Sponsor has consulted with FDA.

Study restart will occur following approval of the IRB/REC and/or FDA as applicable.

Guidelines for assessing relatedness are detailed in Section 7.1.5.

### **7.3.3 Unblinding**

This is a double-blind study.

Emergency unblinding for AEs may be performed. This option may be used ONLY if the patient's well-being requires knowledge of the patient's treatment assignment. Unblinding should only be considered for the safety of the patient. If unblinding is deemed necessary by the Investigator, the Investigator can unblind the patient's treatment allocation after discussion and approval by Sponsor Medical Monitor. The Investigator must note the date, time, and reason for unblinding. The Investigator should inform the Sponsor that the patient was unblinded, however they are not required to reveal to the Sponsor the patient's treatment allocation.

Unblinded information will only be accessible to those who need to be involved in the safety reporting to Health Authorities, Ethics Committees, and/or IRBs.

Investigators will receive only blinded information unless unblinded information is judged necessary for safety reasons.

## **8. STATISTICAL METHODS and CONSIDERATIONS**

Prior to the analysis of the final study data, a detailed Statistical Analysis Plan (SAP) will be written describing all analyses that will be performed. The SAP will contain any modifications to the analysis plan described below.

### **8.1 Data Sets to be Analyzed**

Any participant who is randomized to a treatment allocation will be considered part of the intention-to-treat (ITT) population. The ITT population will be used for the summary of all demographic and baseline characteristics and for analysis of the primary outcome. Subjects lost to follow-up, requiring rescue therapy, those who discontinue study prior to completion of the primary treatment

end point (Week 4) and those who test positive for SARS-CoV-2 infection at Weeks 2 or 4 will be considered as treatment failures. Separate analysis will examine treatment failures in the period between the cessation of study treatment (Week 4) and the end of study (Week 6). All deaths will be considered as treatment failures. All subjects will be grouped in analyses and summaries based on their randomization allocation. The following analysis populations will be defined from the ITT population:

- The safety analysis set includes all randomized participants and is synonymous with the ITT set except that patients will be grouped based on treatment actually received.
- Per-protocol (PP) analysis set includes all participants who complete the trial and who receive ≥90% Study Treatments through to either diagnosis of SARS-CoV-2 infection (study end point) or to end of study for those without a SARS-CoV-2 diagnosis, based on subject completed accountability logs, and have no significant protocol violations. Participants in this sample will be grouped to treatment arms they actually received. This set will be used as a sensitivity analysis to summarize the primary and secondary efficacy outcomes.

## **8.2 Demographic and Other Baseline Characteristics**

Demographic and baseline data, vital signs, medical history, concomitant illnesses, and current medications/treatments will be summarized by means of descriptive statistics: continuous variables as mean, median, standard deviation, and interquartile ranges and categorical variables as frequencies and percentages, stratified by treatment arm based on the ITT population.

## **8.3 Safety Analysis**

All safety and tolerability summaries will be performed on the safety analysis population.

### **8.3.1 Adverse events**

Treatment emergent AEs will be summarized by frequencies and will be presented by system organ class and preferred term with the number and percentage of participants affected. Frequencies will be presented with respect to maximum severity and to strongest relationship to Study Treatment. Multiple occurrences of the same AE will be counted only once following a worst-case approach with respect to severity and relationship to Study Treatment.

The proportion of participants experiencing any AEs (Grade 1-4) following treatment with study drug will be presented as part of the safety analysis set. The precision with which this sample result estimates the rate of similar AEs in the population represented by the study sample will be reported in terms of 95% confidence intervals (CI) around the sample proportions. This will provide 95% confidence that the rate of severe adverse effects is not greater than the upper limit of the CI around the proportion of participants with grade 3+ events in the study sample.

### **8.3.2 Laboratory Data**

Continuous response variables per time point and changes from baseline will be summarized with mean, median, minimum, and maximum values. Categorical response variables will be summarized per time point with percentages.

## **8.4 Efficacy Analysis**

The primary efficacy analysis is the difference between groups of confirmed SARS-CoV-2 infection as based on the ITT analysis population.

---

## 8.5 Secondary Analysis

Secondary outcomes will be summarized as to the incidence of each symptom by treatment group and the average number of days each symptom was present over the course of the study (6 weeks). Summaries will be presented, noncumulatively by visit and well as cumulatively over 4 weeks of treatment.

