## **6.7 Definition of confirmed SARS-CoV-2 infection and SARS-CoV-2 symptom score**

Participants will be queried as to any new diagnosis of SARS-CoV-2 infection, defined as a positive PCR test for SARS-CoV-2. This definition is consistent with the current protocol for viral PCR testing. All deaths will be considered as treatment failures.

Participants will also be instructed to maintain a symptom diary that includes those symptoms considered common for SARS-CoV-2. The diary is inclusive of symptoms identified by the World Health Organization for a diagnosis of SARS-CoV-2 as well as more recently identified symptoms such as conjunctivitis, diarrhea, and loss of taste or smell. Each symptom will be scored as present (score of 1) or absent (score of 0) for each two week interval and the incidence of each symptom will be summarized by treatment group. In addition, the average number of days subjects had each symptom throughout the study period (6 weeks) will be summarized by treatment group.

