### **8.4. Analysis of the Secondary Efficacy Endpoint**

The incidence of each symptom will be summarized by treatment group for each two week interval. In addition, the average number of days subjects had each symptom throughout the study period (6 weeks) will be summarized by treatment group. Summaries will be presented noncumulatively by visit as well as cumulatively over 4 weeks of treatment. The secondary analysis will be performed for the ITT population.

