## **9.1. Adverse Events**

An adverse event (AE) is defined as any unfavorable and unintended change in the structure, function, or chemistry of the body, or worsening of a pre-existing condition, temporally associated with the use of a product whether or not considered related to the use of the product. In this study, such changes will be monitored, classified, and summarized, as Clinical or Laboratory AEs. Medical conditions/diseases present before starting the investigational drug will be considered adverse events only if they worsen after starting study treatment. Verbatim terms on CRFs will be mapped to preferred terms (PTs) and system organ classes (SOCs) using the Medical Dictionary for Regulatory Activities (MedDRA) (version 23.0).

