>80%	x (xx.x%)	x (xx.x%)

Site 101

.

Site 108

.

[1] Duration of exposure is defined as the date of last dose minus the date of first dose + 1.

[2] Treatment compliance is defined as the total number of doses taken divided by the total number of planned doses times 100.

Reference: Listing 16.2.5.1 and Listing 16.2.1

Table 14.2.1.1  
Incidence of SARS-CoV-2 Infection by Visit  
(ITT Population)

	GLS-1200 (N=XX)	Placebo (N=XX)	p-value [1]
Treatment Success [2]	x (xx.x%)	x (xx.x%)	
Treatment Failure [3]	x (xx.x%)	x (xx.x%)	
Lost to follow-up	x (xx.x%)	x (xx.x%)	
Required rescue therapy	x (xx.x%)	x (xx.x%)	
Discontinued study prior to completion of Week 4	x (xx.x%)	x (xx.x%)	
Tested positive for SARS-CoV-2 infection at any time up to Week 4	x (xx.x%)	x (xx.x%)	
Had missing PCR result at any visit up to Week 4	x (xx.x%)	x (xx.x%)	
Died	x (xx.x%)	x (xx.x%)	
Week 0 PCR Result			
n	x	x	
Negative	x (xx.x%)	x (xx.x%)	
Positive	x (xx.x%)	x (xx.x%)	
Missing	x (xx.x%)	x (xx.x%)	
Week 2 PCR Result			
n	x	x	
Negative	x (xx.x%)	x (xx.x%)	
Positive	x (xx.x%)	x (xx.x%)	
Missing	x (xx.x%)	x (xx.x%)	
...			

[1] The p-value is calculated using a Fisher's exact test.

[2] Subjects who test negative for SARS-CoV-2 infection at Weeks 2 and 4 are considered treatment successes.

[3] Subjects who met any of the reasons listed are considered treatment failures. Subjects who fail treatment for multiple reasons are counted once for each reason.

Reference: Listing 16.2.6.1

Source: \\xx\\xxx\\xxx\\xxx\\xxxxxx\\xxxxxxxxxxxx\\xxxx\\xxxxx.sas      date      time

**Programming note: Continue for remaining visits. Repeat for Table 14.2.1.2 Incidence of SARS-CoV-2 Infection (PP Population).**

Table 14.2.2  
Incidence of Individual Symptoms and Average Number of Days with Symptoms by Visit Interval  
(ITT Population)

Symptom	GLS-1200 (N=XX)	Placebo (N=XX)
Subjects who reported Body Aches at least once from Day 1 to Week 2	x (xx.x%)	x (xx.x%)
Subjects who reported Body Aches at least once from Week 2 to Week 4	x (xx.x%)	x (xx.x%)
Subjects who reported Body Aches at least once from Week 4 to Week 6	x (xx.x%)	x (xx.x%)
Subjects who reported Body Aches at least once during the overall treatment phase [1]	x (xx.x%)	x (xx.x%)
Number of days subjects reported Body Aches from Day 1 to Week 2		
n	x	x
Mean (SD)	xx.x (xx.xx)	xx.x (xx.xx)
Median	xx.x	xx.x
Min, Max	xx, xx	xx, xx
Number of days subjects reported Body Aches from Week 2 to Week 4		
n	x	x
Mean (SD)	xx.x (xx.xx)	xx.x (xx.xx)

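### The symptom *incidence* in the secondary analysis is a period prevalence: it mixes new onset with symptoms present before the first dose

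*Protocol*

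**What the plan says.** Protocol 8.5 defines the secondary analysis: "Secondary outcomes will be summarized as to the incidence of each symptom by treatment group", together with the average number of days each symptom was present. Protocol 6.7 gives the scoring: "Each symptom will be scored as present (score of 1) or absent (score of 0) for each two week interval". SAP 8.4 repeats it: "The incidence of each symptom will be summarized by treatment group for each two week interval". It then adds: "Summaries will be presented noncumulatively by visit as well as cumulatively over 4 weeks of treatment".

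SAP Appendix C, Table 14.2.2, turns this into a counting rule. Its first row reads "Subjects who reported Body Aches at least once from Day 1 to Week 2" and its second "Subjects who reported Body Aches at least once from Week 2 to Week 4". A third row covers Week 4 to Week 6, and a fourth covers the whole treatment phase, Day 1 to Week 4. A footnote bases the percentages on the ITT population.

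None of these places requires the symptom to be absent before dosing, defines a first onset, or removes from the denominator participants who already have it. The adverse event analysis does have a rule for pre-existing conditions (SAP 9.1): "Medical conditions/diseases present before starting the investigational drug will be considered adverse events only if they worsen after starting study treatment".

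**The concern.** Incidence normally means new cases among people at risk of becoming one. Here a participant with long-standing sneezing or headache enters as a positive on the first diary day.

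Such participants are to be expected. The diary items (SAP Listing 16.2.6.2) include headache, fatigue, runny nose, sneezing and GI issues. The eligibility criteria (Protocol 4.2 and 4.3) exclude nobody for current symptoms. Participants whose enrollment swab is PCR-positive are asked to stay in (Protocol 6.5), so symptoms of an infection acquired before dosing are counted too. Dosing starts straight after randomization (Protocol 3), and no pre-dose symptom entry is described.

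The secondary objective is symptoms consistent with SARS-CoV-2 infection, by arm. Pre-existing symptoms add roughly equal counts to both arms, shrink the difference that prevention would produce, and add variance. With 150 v 75 participants, a chance difference in pre-dose symptoms would also show up in the table, and no baseline symptom row is planned that would let a reader see it.

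**Working it through.** **The plan's own figures.** The plan gives no rate or power for any symptom, so there is no symptom figure to reproduce. Its only design figure is the 80.8% power for the primary endpoint (Protocol 8.7). A two-sided continuity-corrected z test, enumerated exactly at 10% v 1% with 75 v 150, gives 80.9%. The point here does not depend on it.

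**Inputs**
- From the documents: 150 GLS-1200 and 75 placebo; infection 1% v 10% (Protocol 8.7).
- Assumed: 60% of infected participants report the symptom, so COVID-related onset is e = 0.60 × 10% = 6% on placebo and 0.60 × 1% = 0.6% on GLS-1200.
- Assumed: pre-dose prevalence b = 20% in both arms, with the symptom persisting (range 10% to 30%).
- Assumed: onset from other causes r, equal in both arms, among those symptom-free at Day 0 (range 0 to 30%).

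**Formulas**
- Onset among the symptom-free: o = 1 − (1 − e)(1 − r).
- Planned any-report proportion: p = b + (1 − b)·o, with n = 75 and 150.
- First-onset proportion: o, with n = 75(1 − b) and 150(1 − b), which is 60 and 120 at b = 20%.
- SE of the difference, unpooled: √[p₁(1 − p₁)/n₁ + p₂(1 − p₂)/n₂].

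**Worked case, b = 20%, r = 0**
- Planned: placebo 0.20 + 0.80 × 0.06 = 24.8%; GLS-1200 0.20 + 0.80 × 0.006 = 20.5%. Difference 4.32 points, SE 5.98, ratio 0.72.
- First onset: 6.0% v 0.6%. Difference 5.40 points, SE 3.15, ratio 1.72.

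**Varying r at b = 20%** (placebo v GLS-1200; difference and SE in points)

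| r | Planned | Diff / SE | Ratio | First onset | Diff / SE | Ratio |
|---|---|---|---|---|---|---|
| 0 | 24.8% v 20.5% | 4.32 / 5.98 | 0.72 | 6.0% v 0.6% | 5.40 / 3.15 | 1.72 |
| 10% | 32.3% v 28.4% | 3.89 / 6.54 | 0.59 | 15.4% v 10.5% | 4.86 / 5.44 | 0.89 |
| 20% | 39.8% v 36.4% | 3.46 / 6.88 | 0.50 | 24.8% v 20.5% | 4.32 / 6.68 | 0.65 |
| 30% | 47.4% v 44.3% | 3.02 / 7.05 | 0.43 | 34.2% v 30.4% | 3.78 / 7.43 | 0.51 |

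Varying b from 10% to 30% with r = 0 gives planned ratios of 1.0 to 0.6 and first-onset ratios of 1.8 to 1.6. First onset is the sharper measure in every case, but most of the apparent gain depends on r being near zero.

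**Chance imbalance.** At b = 20% the SE of the between-arm difference in pre-dose prevalence is √[0.20 × 0.80 × (1/75 + 1/150)] = 5.7 points, larger than the 4.32-point difference expected under the planned count.

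**Recounting.** Assume 10% of participants have a persistent symptom and onset is 5% per interval among the rest, with short episodes. Each interval row then reads 0.10 + 0.90 × 0.05 = 14.5%. The three rows together hold 43.5 positives per 100 participants, of which 3 × 0.90 × 5 = 13.5 are onsets. The Day 1 to Week 4 row counts each participant once, but still includes the pre-existing 10%.

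**The case against.** A reader might infer that the table measures background prevalence instead of onset, recounts continuing symptoms throughout, and biases the comparison. The documents do not support that.

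- **Mixture.** The any-report count contains onset as well as background. The share of each depends on rates that the plan does not give.
- **Recounting.** It occurs only in the rows that the plan itself calls non-cumulative, and no document adds them up.
- **Symptom days.** The average number of days with a symptom is a burden measure, so counting continuing days is its definition and not an error.
- **No systematic bias.** Randomization balances pre-dose symptoms in expectation. SAP 8.4 only summarizes; the Fisher test in SAP 8.2 belongs to the primary endpoint. The primary endpoint and sample size are unaffected.
- **Size.** A reader might also take the move from 0.72 to 1.72 as the gain from the fix. It requires that nobody develops headache, sneezing or fatigue for another reason during treatment.

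There is partial mitigation. Significant illnesses of the last 6 months are recorded (Protocol 6.2.2) and summarized by arm (SAP 7.4). The daily dated entries in Listing 16.2.6.2 allow the first report after dosing to be derived. SAP 1 cites a symptom diary form that is not among the documents, so it may already have a Day 0 entry. The adverse event parallel is also imperfect: that rule turns on worsening, which a 0/1 diary cannot record.

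All of this stands and limits the point. None of it supplies an onset condition for a table headed as incidence. Medical history by diagnosis also does not show who had which diary symptom on Day 0.

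**Conclusion.** The point holds as one of definition and labelling, with a modest loss of sharpness. Protocol 6.7 and 8.5 and SAP 8.4 with Table 14.2.2 give the name incidence to a period prevalence over the full ITT population. The consequences are dilution of the contrast for symptoms of new infection and exposure to chance baseline imbalance.

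At 20% pre-dose prevalence and 6% v 0.6% COVID-related onset, the first-onset ratio is about 2.4 times the planned one when non-COVID onset is zero (1.72/0.72), 1.5 times at 10% (0.89/0.59), 1.3 times at 20% (0.65/0.50) and 1.2 times at 30% (0.51/0.43). From 10% upward it stays below 1 under either count, so neither version would show a difference clearly. All these rates are assumptions except the 10% v 1% infection rates and the arm sizes. The finding rests on the absence of a rule in the protocol and SAP; the diary form itself could not be checked.

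This is a worthwhile, inexpensive improvement to a descriptive secondary table. It is not a flaw in the trial's main comparison.

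**What to change.** 1. Have the symptom diary completed once on Day 0 before the first spray, unless the form already requires it.
2. In SAP 8.4 and Table 14.2.2, add for each symptom a first-onset row over Day 1 to Week 4 and one per interval, among participants free of that symptom at Day 0. An episode counts only in the interval in which it starts.
3. Report Day 0 prevalence of each symptom by arm.
4. Keep the existing any-report rows on the ITT denominator, relabelled as period prevalence, and align the wording of Protocol 6.7 and 8.5.
5. Leave the symptom-days summary as it is.

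The cost is one diary instruction and some SAP and table wording, with no extra visit or sample and no planned output lost. There are two downsides. Denominators become symptom-specific, so a participant with a trivial Day 0 symptom leaves that first-onset row even if a later infection brings the same symptom; the retained rows still show such a participant. A single Day 0 entry will also miss some intermittent chronic symptoms that happen to be absent that day.
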